6.7 BASELINE, TIME WINDOWS AND CALCULATED VISITS

patients for whom both sources of information are available (eCRF and

For all efficacy endpoints, "baseline" is defined as the assessments done at Visit 2, prior to administration of first dose. If this value is not available, the latest measurement prior to treatment administration will be used.

For demographics, medical history, concomitant antipsychotic medication, AEs, concomitant therapies, vital signs and C-SSRS, Visit 1 (screening) will be considered as "baseline". If this value is not available, the earliest value prior to treatment administration will be used.

Visit will be labelled according to the flow chart in the protocol: Visit 1 (for screening), Visit 2 (randomization and start of treatment), Visits 3-19, End of Treatment (EOT), Follow Up (FU) (28 days after Visit 16 for completed patients; 28 days after EOT for early discontinued patients). Planned and actual test days will be calculated relative to the beginning of study as indicated in the following table.

Table 6.7: 1 Visit calculation relative to study start

Visit	Relative to study start			
	Planned test day (every 14 days)	Actual test day		
2	1	1		

TSAP for BI Trial No: 1289-0049 Page 20 of 35

Proprietary confidential information © 2021 Boehringer Ingelheim International GmbH or one or more of its affiliated companies

Visit	Relative to study start			
	Planned test day (every 14 days)	Actual test day		
3	15	Visit 3 date – first dose date +1		
4	29	Visit 4 date – first dose date +1 Visit 5 date – first dose date +1		
5	43			
Etc				
16	197	Visit 16 date – first dose date +1		
T/W 17	Visit 16 + 2 days	T/W 17 date – first dose date + 1		
T/W 18	Visit 16 + 4 days	T/W 18 date – first dose date + 1		
EOT (T/W 19)	Visit 16 + 7 days	EOT (T/W 19 date) – first dose date + 1		
FU	Visit 16 + 28 days	FU date – first dose date + 1		

All time to event analyses will use the visit start date as recorded on the CRF as the analysis date.

7. PLANNED ANALYSIS

For End-Of-Text (EoT) tables, the set of summary statistics is: N / Mean / SD / Min / Median / Max.

For tables that are provided for endpoints with some extreme data, median, quartiles and percentiles should be preferred to mean, standard deviation, minimum and maximum.

Tabulations of frequencies for categorical data will include all possible categories and will display the number of observations in a category as well as the percentage (%) relative to the respective treatment group (unless otherwise specified, all subjects in the respective subject set whether they have non-missing values or not).

The precision for percentages should be one decimal point, unless the denominator is smaller than 100 (in all treatment columns), in which case percentages are given in integer numbers. The category missing will be displayed only if there are actually missing values.

7.1 DEMOGRAPHIC AND OTHER BASELINE CHARACTERISTICS

Only descriptive statistics are planned for this section of the report based on the treated set.

7.2 CONCOMITANT DISEASES AND MEDICATION

Only descriptive statistics are planned for this section of the report, based on the treated set. A summary of concomitant diseases will be provided by treatment group, System Organ Class (SOC) and Preferred Term (PT).

Concomitant medications will be summarized by two groups: schizophrenia and non-schizophrenia. And depending on if concomitant medication is started before or after trial medication, baseline and on-treatment concomitant medication use will be summarized separately.

7.3 TREATMENT COMPLIANCE

Only descriptive statistics are planned for this section of the report. Summary statistics will be given for percent compliance along with the number (%) of patients with compliance in the categories <80%, 80% - 100%, >100%, see more details in Section 5.4.2.

Proprietary confidential information © 2021 Boehringer Ingelheim International GmbH or one or more of its affiliated companies

7.4 PRIMARY ENDPOINT(S)

The hypothesis testing strategy for primary and key secondary endpoints is described in **Section 7.2 of the CTP:**

The trial will follow a hierarchical testing strategy. The first hypothesis for the superiority testing of the primary endpoint time to first relapse is $(HR = hazard\ ratio)$:

 H_o : $HR_{BI\ 409306\ /placebo} = 1$ vs. H_a : $HR_{BI\ 409306\ /placebo} \neq 1$, where $HR_{BI\ 409306\ is}$ the hazard ratio for the pooled active treatment arms (i.e. BI 409306 50 mg q.d. and BI 409306 25 mg q.d.), over 28 weeks (excluding the withdrawal/taper period)

Superiority will be declared if the hazard ratio between BI 409306 vs. placebo is statistically significantly less than 1 at the two-sided type I error level $\alpha = 0.05$.

If the first hypothesis test is determined to be statistically significant, the individual doses will be tested for superiority using Hochberg's step-up test. The method will be to perform the statistical tests and rank the p-values for the individual doses vs. placebo. Let $p_{(1)} \ge p_{(2)}$ be the two-sided p-values. The corresponding null hypotheses are $H_{0(1)}$ and $H_{0(2)}$.

 $H_{0(1)}$: $HR_{BI\ 409306\ /\ placebo} = 1$ vs. $H_{a(1)}$: $HR_{BI\ 409306\ /\ placebo} \neq 1$, where $HR_{BI\ 409306\ is}$ the hazard ratio for the BI 409306 dose with the highest p-value

 $H_{0(2)}$: $HR_{BI\ 409306\ /\ placebo} = 1$ vs. $H_{a(2)}$: $HR_{BI\ 409306\ /\ placebo} \neq 1$, where $HR_{BI\ 409306\ is}$ the hazard ratio for the BI 409306 dose with the lowest p-value

Step 1: If $p_{(1)} \le 0.05$ then both hypotheses are rejected and both doses are declared statistically significant and testing ends. If $p_{(1)} > 0.05$, then $H_{0(1)}$ is not rejected and the testing proceeds to Step 2.

Step 2: If $p_{(2)} \le 0.025$, then $H_{0(2)}$ is rejected and this dose is declared statistically significant. If $p_{(2)} > 0.025$, then all doses fail.

7.4.1 Primary efficacy analysis

The primary analysis will be conducted on the FAS using the ITT follow-up period as defined in Section 6.1. Because the ITT covers the 28 weeks of planned treatment and not the T/W period, the treatment arms will be pooled according to dose and disregarding the T/W randomization.

Revised CTP in Section 7.3.1:

The equality of the hazard rates will be tested by the Wald test for the treatment effect in a stratified Cox proportional hazards model at the two-sided 5% significance level. The model includes the treatment effect as the only covariate and is stratified by country. Breslow's method for handling ties will be used.

The same stratified Cox proportional hazards model will be used to estimate the hazard ratio of BI 409306 vs. placebo and the asymptotic 95% Wald confidence interval. A hazard ratio of less than one favors BI 409306. The analysis will be implemented using SAS® PROC PHREG. Cox proportional hazard model assumptions will be verified.

In early discontinued patients, if the occurance of a relapse cannot be determined between the time of discontinuation and last contact, it is assumed that no relapse has occurred. Patients who discontinue study medication will be followed until the end of the trial for the primary endpoint. Patients who are lost-to-follow up will be censored for the primary endpoint at the date of last known patient contact.

According to the CTP, we have specified more details regarding efficacy analysis using ITT FU and Full FU:

Definition of last at-risk date:

The last at-risk date determined as the latest date among: the date of first dose of study medication, the date of last drug administration, all the visit start dates (including phone contact dates in which the patient was reached and follow-up contact dates) and start or stop dates of events reported on the adverse event forms.

If a patient dies, the date of death is their last at-risk date.

Definition of Visit 16 date:

The date of Visit 16 for the determination of the ITT FU period end date will be the start date recorded on eCRF.

Time to event calculations:

A. Patients completing treatment period and study period (for ITT analysis):

Events (relapses) are counted in the ITT time to event analysis whenever they occur between the first dose of randomized treatment and the patient's Visit 16 date or the date of last dose if this occurred after visit 16. (In SDTM this is EPOCH=TREATMENT1)

- Patients with event counted: <date of event> <date of first drug administration> +1 day
- Patients without event counted: <date of last dose of study drug or date of Visit 16> <date of first drug administration >+1 day
- B. Patients completing treatment period and study period (for Full FU analysis): Events (relapses) are counted in the FU time to event analysis whenever they occur between the first dose of randomized treatment and the patient's EOS date.
 - Patients with event counted: <date of event> <date of first drug administration> +1 day

- Patients without event counted: <date of EOS> <date of first drug administration
- C. Patients who chose Early Discontinuation Option 1 or Option 2 per CTP (ITT and Full FU analysis):
- And completed required study period: Events (relapses) are counted in the time to event analysis whenever they occur between the first dose of randomized treatment and the patient's EOS date.
 - Patients with event counted: <date of event> <date of first drug administration> +1
 - Patients without event counted: <date of EOS> <date of first drug administration >+1 day
- And discontinued or did not complete required study period: Events (relapses) are counted in the time to event analysis whenever they occur between the first dose of randomized treatment and the patient's last at-risk date.
 - Patients with event counted: <date of event> <date of first drug administration> +1 day
 - Patients without event counted: <date of last at-risk date > <date of first drug administration >+1 day
- Patients who chose Early Discontinuation Option 3 or Option 4 per CTP (ITT and D. Full FU analysis):
- And completed required study period: Events (relapses) are counted in the time to event analysis whenever they occur between the first dose of randomized treatment and the patient's End of Study Date.
 - Patients with event counted: <date of event> <date of first drug administration> +1
 - Patients without event counted: < date of EOS > < date of first drug administration >+1 day
- And discontinued or did not complete required study period: Events (relapses) are counted in the time to event analysis whenever they occur between the first dose of randomized treatment and the date of last at-risk date.
 - Patients with event counted: <date of event> <date of first drug administration> +1
 - Patients without event counted: < date of last at-risk date > < date of first drug administration >+1 day
- Patients who chose Early Discontinuation Option 5, i.e. withdrew consent per CTP (for ITT and Full FU analysis): Events (relapses) are counted in the time to event analysis whenever they occur between the first dose of randomized treatment and the patient's date of consent withdrawal.
 - Patients with event counted: <date of event> <date of first drug administration> +1
 - Patients without event counted: <date of consent withdrawal> <date of first drug administration >+1 day
- Patients who are Lost-to-Follow-up (for ITT analysis): Events (relapses) are counted in the time to event analysis whenever they occur between the first dose of randomized treatment and the last at-risk date.

- Patients with event counted: <date of event> <date of first drug administration> +1 day
- Patients without event counted: <date of last at-risk> <date of first drug administration >+1 day

*Please note: Patients who are LTFU during the study (regardless of initial Early Discontinuation choice), but were successfully found towards the end of study via a vital status call, will be included in the Full-FU analysis period by replacing as follows:

• Patients without event counted: <date of vital status/date of EOS> – <date of first drug administration >+1 day

The following SAS code will be used:

```
proc phreg data= primary;
   CLASS &trt.(ref="Placebo") / order=internal;
   model aval*cnsr(1) = &trt./ties=breslow;
   strata countrdc;
   hazardratio 'HR' &trt. /diff=ref cl=both;
run;
```

Subgroup analyses will be performed on the subgroups specified in Section 6.4. Definition of Japanese patients is provided in Section 9.1. The same model as described above for the primary efficacy analysis, will be used for these analyses.

The following SAS code will be used for survival plot:

```
proc lifetest data=primary method=km plots=survival(failure test
atrisk);
time aval*cnsr(1);
id usubjid;
strata &trt. /test=logrank;
run;
```

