#### 4.1.4 Drug assignment and administration of doses for each patient

Following the screening period, patients who qualify according to entry criteria will be randomised to one of the three treatment groups to be evaluated as outlined in [Table 4.1.4: 1](#).

Dispensing of kits for the double-blind treatment period will begin at Visit 2. Trial medication kits will be provided as described in the [Flow Chart](#). At each of these visits, medication assignment will be provided through IRT. The assigned medication number(s) must be entered in the eCRF, and the corresponding medication kit(s) must be given to the patient.

To maintain the blind, all treatments will consist of two tablets of BI 409306 or placebo during the 28 week treatment period, and 1-4 tablets per day during the withdrawal/taper period.

Table 4.1.4: 1 Dosage and treatment schedule for 28 week treatment period

Treatment Group	Dose	Total tablets per daily dose
Placebo	n/a	2 tablets in P.M. (1 25 mg placebo tablet; 1 50mg placebo tablet)
BI 409306	25 mg	2 tablets in P.M. (1 25 mg BI 409306 tablet; 1 50mg placebo tablet)
BI 409306	50 mg	2 tablets in P.M. (1 25 mg placebo tablet; 1 50mg BI 409306 tablet)

Table 4.1.4: 2 Dosage and treatment schedule for 7 day withdrawal/taper period

	Placebo	BI 409306 25 mg abrupt withdrawal	BI 409306 25 mg slow taper	BI 409306 50 mg abrupt withdrawal	BI 409306 50 mg slow taper
Day 1 4 tablets in P.M.	4 x 10 mg placebo tablets	4 x 10 mg placebo tablets	2 x 10 mg BI 409306 tablets; 2 placebo tablets	4 x 10 mg placebo tablets	4 x 10 mg BI 409306 tablets
Day 2 3 tablets in P.M.	3 x 10 mg placebo tablets	3 x 10 mg placebo tablets	2 x 10 mg BI 409306 tablets; 1 placebo tablet	3 x 10 mg placebo tablets	3 x 10 mg BI 409306 tablets
Day 3 3 tablets in P.M.	3 x 10 mg placebo tablets	3 x 10 mg placebo tablets	2 x 10 mg BI 409306 tablets; 1 placebo tablet	3 x 10 mg placebo tablets	3 x 10 mg BI 409306 tablets
Day 4 2 tablets in P.M.	2 x 10 mg placebo tablets	2 x 10 mg placebo tablets	1 x 10 mg BI 409306 tablet; 1 placebo tablet	2 x 10 mg placebo tablets	2 x 10 mg BI 409306 tablets
Day 5 2 tablets in P.M.	2 x 10 mg placebo tablets	2 x 10 mg placebo tablets	1 x 10 mg BI 409306 tablet; 1 placebo tablet	2 x 10 mg placebo tablets	2 x 10 mg BI 409306 tablets
Day 6 1 tablet in P.M.	1 x 10 mg placebo tablet	1 x 10 mg placebo tablet	1 x 10 mg BI 409306 tablet	1 x 10 mg placebo tablet	1 x 10 mg BI 409306 tablet

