### 7.3 PLANNED ANALYSES

Two patient populations are defined:

- The treated set (TS) includes all patients who were dispensed study medication and were documented to have taken at least one dose of investigational treatment
- The full analysis set (FAS) includes all patients in the treated set with at least one post-baseline measurement of any type

No per protocol population will be used for analyses; however protocol violations will be identified and listed.

Analysis sets will be fully defined in TSAP.

Three analysis periods are defined:

- **Intent to Treat (ITT) follow-up:** from treatment start date until the end of the intended complete treatment period:

For patients who complete the trial according to the [flow chart](#), the withdrawal/taper period is not included. Additionally, if a patient happens to take drug for 29 weeks (i.e. 1 week longer than the planned 28 weeks) and then begin the withdrawal/taper period, the withdrawal/taper period will not be included.

For patients who discontinue prior to the 28 week treatment period, e.g. at week 25, the follow-up period until the end of week 28, is included.

- **Full follow-up:** from randomisation until the end of the trial, including all observed time on and off trial medication until the follow-up visit or the last date of contact:

For patients who discontinue trial medication according to the [flow chart](#), the withdrawal/taper period is included. Additionally, if a patient happens to take drug for 29 weeks (i.e. 1 week longer than the planned 28 weeks) and then begin the withdrawal/taper period, the withdrawal/taper period is included.

For patients who discontinue prior to the 28 week treatment period, e.g. at week 25, the follow-up period until the last contact date is included.

The full follow-up analysis period will be used as a sensitivity analysis to the ITT follow-up analysis.

- **On-treatment:** from treatment start date until the date of discontinuation of trial medication + 7 days:

For all patients this analysis period includes only the time on trial medication + 7 days after taken off trial medication.

For patients randomised to the withdrawal period, this will include 28 weeks of treatment, or for early discontinued patients, the time period on active treatment prior to discontinuation + 7 days, which corresponds to the 7 days abrupt withdrawal period.

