5.4.2 Treatment compliance and treatment exposure

Treatment compliance:

Treatment compliance is assessed via the use of the AICURE device and the eCRF. Average adjusted compliance will be calculated and displayed. Compliance will be categorized into classes: <80%, >=80% to <=100%, >100%.

Treatment exposure:

- Exposure is calculated as (drug stop date) (drug start date) +1
- Treatment exposure classes (<=102 days, 103 days to <=204 days, >204 days)

The Taper/Withdrawal (T/W) period is included in the treatment exposure calculation.

Study observation periods:

• Each patient's observation time contribution, for the Intent to Treat (ITT) follow-up, and Full follow-up period, will be summarized, for more details see Section 6.1.

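### Read literally, SAP 7.4.1 rule A lets the excluded taper/withdrawal week into the primary ITT window for completers

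*SAP*

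**What the plan says.** **The exclusion.** Protocol 7.2 states the primary hypothesis over 28 weeks without the T/W period. Protocol 7.3 defines the ITT follow-up period and says that for patients who complete per the flow chart "the withdrawal/taper period is not included". It adds that T/W stays out even if main treatment overruns to 29 weeks. SAP 6.1 and 6.6 repeat the exclusion. SAP 7.4.1 opens the same way: "Because the ITT covers the 28 weeks of planned treatment and not the T/W period", arms are pooled by dose.

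**Rule A.** Later in SAP 7.4.1, completers' relapses count from first dose to the "Visit 16 date or the date of last dose if this occurred after visit 16", with the bracketed note "In SDTM this is EPOCH=TREATMENT1". For completers without an event, time runs to the "date of last dose of study drug or date of Visit 16". That line carries no epoch note.

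**What completers take after Visit 16.** Flow Chart footnote 16 has the one-week wallet dispensed to patients who complete 28 weeks, and the wallet is marked at Visit 16. Protocol 4.1.4 specifies "1-4 tablets per day during the withdrawal/taper period". Flow Chart footnote 4 calls these tablets study drug. SAP 5.4.2 computes exposure to the drug stop date and says: "The Taper/Withdrawal (T/W) period is included in the treatment exposure calculation".

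**The concern.** A primary-endpoint derivation should give one end date per patient, and that date should match the stated estimand. Rule A does not secure either. If the last dose means the last study tablet, nearly every completer's window ends about 7 days after Visit 16, inside the period that the protocol excludes.

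That week differs from the preceding 28. By design, half of the active-arm completers are switched abruptly to placebo tablets and the other half are tapered. The flow chart also schedules the C-SSRS at Visits 17, 18 and 19, three times in 7 days against every two weeks before, and suicidal behaviour or ideation of type 4 or 5 is a relapse criterion. Relapses arising as treatment is withdrawn would be charged to BI 409306 in a hazard ratio meant to describe 28 weeks on treatment.

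Events and censoring could also end on different dates: events limited by the epoch note to the 28-week period, censoring at the last T/W tablet.

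**Working it through.** **Step 1: which dose can fall after Visit 16?** Dosing is in the evening (Protocol 4.1.4). The Visit 16 PK sample is drawn 8 to 24 hours after the last dose taken at home (Protocol 5.3.2.1 and 10.3). On schedule, the last 28-week dose therefore precedes Visit 16, and any later dose comes from the T/W wallet. The exception is a patient who continues the 28-week supply past Visit 16.

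**Step 2: possible readings of rule A for a completer.**

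| Reading | Events counted to | Event-free time to |
|---|---|---|
| Last 28-week dose | about day 197 | about day 197 |
| Last study tablet | up to day 204 | up to day 204 |
| Mixed (epoch limits events only) | about day 197 | up to day 204 |

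Only the first agrees with Protocol 7.2 and 7.3 and SAP 6.1 and 6.6. The second adds up to 7/197 = 3.6% to a completer's window. The mixed reading would hardly move a Cox estimate, because time at risk matters only when some patient has an event in it. It would still distort observation time and numbers at risk.

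**Step 3: reproduce the plan's figure.** Inputs from Protocol 7.7: two-sided alpha 0.05, power 80%, HR 0.50, 258 active and 129 placebo patients, 30% placebo relapse, 20% dropout. Schoenfeld: (1.960 + 0.842)² / [(1/3)(2/3)(ln 0.5)²] = 73.5, rounded up to 74 as stated. With exponential relapse and dropout, the required total is 391 against the stated 385, within 1.5%.

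**Step 4: correct window, 387 patients.** Cumulative hazards over 28 weeks (constant hazard assumed):
- placebo: −ln 0.7 = 0.3567
- active: 0.1783
- dropout: −ln 0.8 = 0.2231

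Expected events = n × λ/(λ+δ) × (1 − e^−(λ+δ)), where λ is the relapse and δ the dropout hazard. The two arms sum to 72.8, and power at HR 0.50 is 79.6%.

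**Step 5: add the T/W week.** Event-free and at risk at week 28:
- placebo: 129 × 0.7 × 0.8 = 72.2
- active: 258 × √0.7 × 0.8 = 172.7

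One-week risk is 1 − e^(−0.3567/28) = 1.27% on placebo and 1 − e^(−0.1783/28) = 0.63% on active.

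| Assumption for the T/W week | Added events | Average HR | Power |
|---|---|---|---|
| HR 0.50 persists | 0.91 + 1.10 = 2.0 (+2.8%) | 0.500 | 80.7% |
| Abrupt-withdrawal half reverts to placebo hazard | 2.6 | 0.507 | 79.4% |
| All active patients revert | 0.91 + 2.19 = 3.1 | 0.514 | 78.0% |

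The average HR weights the log HR of each period by its events. For the last row: 72.8 × ln 0.5 / (72.8 + 3.1) = −0.665, and e^−0.665 = 0.514. With assumed dropout from 35% to 0%, the first row's added events range from 1.6 to 2.5.

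**The case against.** The strongest reply is that the intent is clear enough. The SDTM note points to the 28-week epoch. The dose clause is conditional, which makes sense for a patient who overruns main treatment, the 29-week case in Protocol 7.3. If T/W tablets counted, the Visit 16 alternative would be almost redundant. SAP 4 says that the ITT analysis includes relapses only in the planned 28-week period, SAP 7.8.5 keeps T/W out of the primary analyses, and rule A is offered as detail under the protocol rather than a change to it. The T/W statement in SAP 5.4.2 is specific to exposure. The on-treatment definitions in Protocol 7.3 and SAP 6.1 do not count the abrupt-withdrawal week as time on medication, so those patients need not have a last dose after Visit 16.

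Most of this stands as evidence of intent. A reader might infer that the T/W week does enter the primary analysis; the documents do not support that as fact. They do not settle the opposite either, because TREATMENT1 is nowhere defined and the event-free line has neither an epoch limit nor a rule for choosing its date. If only taper patients had a later last dose, end dates would depend on T/W assignment, which the primary analysis is meant to ignore.

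A reader might also infer a serious loss of power from withdrawal-induced relapses. The documents give no figure for such an excess, so none is assumed beyond reversion to the placebo hazard. The flow chart, whose columns are partly broken, shows no CGI-S mark at Visits 17 to 19. The CGI-S/PANSS criterion would then not be scheduled that week, and 2.0 added events may be high.

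**Conclusion.** The point holds as a defect in the wording of the primary derivation: read literally, rule A gives completers an end date that the rest of the plan excludes, and its two lines can yield different dates. The last 28-week dose is probably what was meant, but the documents do not confirm it.

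The likely effect is small. At 387 patients, the literal reading adds about 2 events to about 73. It leaves the HR at 0.50 and marginally raises power if the treatment effect persists. Full reversion to the placebo hazard in all active patients gives an HR of about 0.514 and power of about 78.0% against 79.6%. These figures rest on constant hazards, exponential 20% dropout and the planning assumptions of Protocol 7.7. SAP 4 says that recruitment stopped early, so actual numbers are unknown; with fewer events, each misassigned one would weigh more. The correction is worth making because it removes a possible bias at almost no cost.

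**What to change.** - In both lines of rule A (event window and event-free formula), set the end date to the later of the Visit 16 date and the last dose of the 28-week treatment medication, with T/W tablets excluded.
- Define EPOCH=TREATMENT1 in the SAP to match, and apply it to both lines.
- State that completers' relapses in the T/W week count only in the Full follow-up analysis.

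The cost is a small change of SAP wording and the matching derivation. No new data are needed.
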